7 STATISTICAL METHODOLOGY

7.1 General Considerations

- For continuous variables, descriptive statistics will include the number of subjects (n), mean, standard deviation (SD), median, minimum, and maximum.
- For categorical variables: number and percentages of subjects will be described.
- For time-to-event variables: number and percentage of subjects with the event using Kaplan-Meier method, the cumulative event rate will be estimated and a plot will be constructed.
- All data processing, summarization, and analyses will be performed using SAS Drug Development (ver. 4.5), and PC-SAS (ver. 9.4) or higher versions.
- Specifications for table, figures, and data listing formats can be found in the TLF specifications for this study.
- For the definition of subgroups of interest can be referred to Section [7.8](#)
- Summaries based on FAS and PPS (e.g. disposition, baseline and efficacy data) will be presented by treatment groups, unless specifically stated otherwise. Safety analysis and other summaries based on SAF will also be presented by treatment groups.

- Initial Randomization Set of efficacy analyses are those of the efficacy data up to Week 12 and include the primary analysis (ACR20 at Week 12/ET) as described 7.4.1.1. This set will be analyzed by the initially treated groups (ASP015K 100 mg, ASP015K 150 mg, Placebo and Reference group) and statistical testing will be performed for ASP015K 100 mg, and 150 mg, compared with Placebo.

Table 3 Initial Randomization Set

Initial Randomization Arm Code	Initial Randomization Label	Analysis Scope
PLACEBO	Placebo	Screening, Week 0 to Week 12, Week 12/ET
100MG	100 mg	
150MG	150 mg	
ETANERCEPT	Etanercept	

- Treatment Sequence Set of analyses are those of the data up to Week 52. Taking into consideration a switch from placebo to active treatment at Week 12, this set will be analyzed by following groups defined below. The two types of "Placebo to ASP015K xx mg at Week 12" groups are not for primary objective and are conducted optionally for efficacy and safety analyses.

Table 4 Treatment Sequence Set

Treatment Sequence Code	Treatment Sequence Label	Week0- Week12	Week 12- Week 52	Analysis Scope
SEQ1	100mg	ASP015K 100 mg	ASP015K 100 mg	Screening, Week 0 to Week 52, EOT
SEQ2	150mg	ASP015K 150 mg	ASP015K 150 mg	
SEQ3	Placebo to 100mg at Week 12	Placebo	ASP015K 100 mg	
SEQ4	Placebo to 150mg at Week 12	Placebo	ASP015K 150 mg	
SEQ5	Etanercept	Etanercept	Etanercept	

- 100 mg: subjects who initially treated as ASP015K 100 mg Group
 - 150 mg: subjects who initially treated as ASP015K 150 mg Group
 - Placebo to 100 mg at Week 12: subjects who initially treated as Placebo group and switched ASP015K 100 mg at Week 12 and at least one dose of ASP015K 100 mg drug after switched
 - Placebo to 150 mg at Week 12: subjects who initially treated as Placebo group and switched ASP015K 150 mg at Week 12 and at least one dose of ASP015K 150 mg drug after switched
 - Etanercept: subjects who initially treated as Etanercept Group
- MedDRA11.1 will be used as the coding dictionary for adverse event and medical history.

- Statistical hypothesis testing will be performed only if specified. All statistical comparisons of treatment groups will be versus placebo (i.e., each ASP015K treatment versus placebo) and will be made using two sided tests at the 0.05 significance level, unless stated otherwise. Multiplicity adjustment will be done in the primary analysis and other analysis if specified.
- Statistical analysis including hypothesis testing for efficacy variables to compare ASP015K 100 mg or ASP015K 150 mg versus Placebo, only the data for the pairwise comparison will be used.
- All statistical results will be presented, as appropriate, by treatment group, by treatment group and scheduled visit; the schedule of assessments is provided in Section 7.11.5-7.
- Demographics and other baseline characteristics will be provided for all ASP015K treatment groups combined ("100 mg + 150 mg") and for all treatment groups, including placebo and reference group, combined ("Total"). Efficacy presentations will not contain combined treatment groups. In study drug exposure, pharmacodynamics and safety presentations, "Total except for Etanercept" will be used in place of "Total".
- Chi-square test is continuity corrected in all analysis.
- Confidence interval for binary outcome is continuity corrected in all analysis.
- Baseline for safety is defined as last non-missing value before the first dose of study drug or reference drug for all subjects including placebo or reference group assigned subjects.
- The values below the lower limit of quantitation (BQL) for β -D-glucan, hCG, Troponin, CK-MB will be treated as it is and these variables are not used for descriptive statistics and displayed in the listings. As for β -D-glucan, it is used for shift-from baseline analysis.
- CRP (mg/dL) is below measurement (i.e. <0.01 mg/dL) then CRP is regarded as 0.01 U/ml, and used for the calculation of DAS28-CRP, etc. and categorized in <1.0 mg/dL.
- Baseline for efficacy is defined as value at Day1 before the first dose of study drug or reference drug for all subjects including placebo or reference group assigned subjects.
- Change from baseline to post-baseline will be calculated as: post-baseline value - baseline value. If the baseline value is missing, then that subject is not included in the calculation at any visit.
- Percent change from baseline to post-baseline will be calculated as: $100 \times (\text{change} / \text{baseline})$. If the baseline value is 0 or missing, or post-baseline value is missing, then percent change from baseline to post-baseline is missing.
- If onset date of AE is Unknown, then missing onset date of AE will be imputed as following steps.
 1. If only the day of the month is missing (e.g., 2013-03), then the first day of the month will be used (2013-03-01),
 2. If both day and month are missing (e.g., 2013), then the first day of January will be used (2013-01-01).
 3. If imputed onset date of AE is earlier than the first date of study drug, then the onset date of AE is onset at the first date of study drug, because AE data in CRF is collected only after the first date of study drug.

- If the start date of concomitant medication is Unknown, then the missing date will be imputed as following steps.
 1. If only the day of the month is missing (e.g., 2013-03), then the first day of the month will be used (2013-03-01),
 2. If both day and month are missing (e.g., 2013), then the first day of January will be used (2013-01-01).

- If the end date of concomitant medication is Unknown, then the missing date will be imputed as following steps.
 3. If only the day of the month is missing (e.g., 2013-03), then the last day of the month will be used (2013-03-31),
 4. If both day and month are missing (e.g., 2013), then the last day of December will be used (2013-12-31).

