4 SAMPLE SIZE

One hundred subjects per group will receive the study drug and 200 subjects the reference drug (a total of 500 subjects).

[Rationale for the sample size]

Based on 015K-CL-RAJ1 result and efficacy result from other RA drugs [XELJANZ[®], tablet, 5 mg, CTD (2013)] [CIMZIA, sc, 200 mg, Syringe, CTD (2012)], 62 subjects per group will provide 90% power to detect a difference assumed in the Step 2 in the closed testing procedure (described in Section 7.4.1.1 Primary Analysis) under the following assumptions. In addition, it is assumed that ACR20 response rate of each country (Japan, Korea and Taiwan) is similar.

- ACR20 response rate at Week 12 in the placebo group: 25%
- ACR20 response rate at Week 12 in the ASP015K 100 mg group: 54.5%

- ACR20 response rate at Week 12 in the ASP015K 150 mg group: 65.5%
- Two-sided significance level of 0.05

On the other hand, according to the Extent of Population Exposure to Assess Clinical Safety for Drugs Intended for Long-term Treatment of Non-life-threatening Conditions (PAB/PCD Notification No.592, dated 24 May 1995), ("the long-term treatment guideline"), a sample size of 300-600 subjects under long-term treatment (6 months) is adequate to observe delayed adverse events at a reasonable frequency (generally, 0.5% to 5%) and to observe whether there is an increase in high-frequency adverse events during the later stage of treatment. For treatment lasting 1 year, 100 subjects is acceptable. It is also described in "Guidelines on methodology for clinical assessment of antirheumatic drugs" (PFSB/ELD Notification No. 0217001, dated 17 February 2006) that 100 subjects for 1 year are necessary.

Therefore, to collect data for 300 subjects for 6 month period, and for 100 subjects for 1 year period in both ASP015K 100 mg and 150 mg groups among 015K-CL-RAJ2/RAJ3/RAJ4 studies as long-term treatment data, approximately 80 subjects per treatment group (400 subjects in total) as a target are necessary to be enrolled in Japan. In addition, the target sample size for Taiwan is set at 10 subjects per treatment group (50 subjects in total) as a target in consideration of the requirement of regulatory authority in Taiwan (10% or more Taiwan subjects) and target sample size for Korea is also set at 10 subjects per treatment group (50 subjects in total) as a target. Therefore, the target sample size per treatment group is set at 100 subjects in total for 3 regions.

[Rationale for the sample size for the reference group]

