5.3 Safety Analysis Set (SAF)

SAF is defined as all subjects who received at least 1 dose of the study drug or reference drug.

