7.5 Analysis of Safety

In general, For AE Analysis up to Week 12 will be performed by Initial Randomization Set in SAF. AE Analysis from "Week 12 to Week 52 or Later" will be performed by Treatment Sequence Set in SAF. AE 100 Patient-Years analysis will be performed by Groups for Patient-Years. Details for analysis groups will be described in 10.3 Appendix 3.

For other safety analysis except for AE up to Week 12 will be performed by Initial Randomization Set in SAF. For other safety analysis except for AE up to Week 52 will be performed by Treatment Sequence Set in SAF. Details for analysis groups will be described in 10.4 Appendix 4.

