10.3 Appendix 3: Overview of AE analysis

Table20, Table21 summarize the analyses of AE occurrence, the analysis of SOC, PT analysis, with "X1", and "X2" indicating that the variable will be analyzed by each defined groups defined footnote. All analyses will be based on the SAF.

Table 20. The overview of AE occurrence analysis

	Overall	Week 0 to Week 12	Week 12 to Week 52 or Later
Number and percentage of subjects with TEAE	X3	X1	X2
Number and percentage of subjects with drug related TEAE	X3	X1	X2
Number and percentage of subjects with death	X3	X1	X2
Number and percentage of subjects with serious TEAE	X3	X1	X2
Number and percentage of subjects with Grade 3 or Higher in Severity TEAE	X3	X1	X2
Number and percentage of subjects with drug related serious TEAE	X3	X1	X2
Number and percentage of subjects with TEAE leading to permanent discontinuation of study drug or reference drug	X3	X1	X2
Number and percentage of subjects with drug related TEAE leading to permanent discontinuation of study drug or reference drug	X3	X1	X2
Number and percentage of subjects with serious TEAE leading to permanent discontinuation of study drug or reference drug	X3	X1	X2
Number and percentage of subjects with drug related serious TEAE leading to permanent discontinuation of study drug or reference drug	X3	X1	X2

Regarding the overview of AE occurrence analysis described above, subgroup analysis based on study region will be also presented.

X1: Placebo, 100mg, 150mg, Reference

X2: 100mg, 150mg, Placebo to 100 mg at Week 12, Placebo to 150 mg at Week12, Reference

X3: 100mg, 150mg, Reference

Table 21. The overview of the number of SOC/PT analysis

	Overall	Week 0 to Week 12	Week 12 to Week 52 or Later
TEAEs	X3 ^{#2}	X1 ^{#2}	X2 ^{#2}
Drug related TEAEs, defined as any TEAE with possible, probable or missing relationship to study drug	X3 ^{#2}	X1 ^{#2}	X2 ^{#2}

as assessed by the investigator.			
Serious TEAEs	X3 ^{#2}	X1 ^{#1}	X2 ^{#2}
Drug related serious TEAEs		X1	
TEAEs by severity based on NCI-CTCAE	X3	X1	
Drug related TEAEs by severity		X1	
Grade 3 or higher TEAEs by severity	X3	X1	
TEAEs by relationship to study drug		X1	
TEAEs leading to death	X3	X1	X2
TEAEs leading to permanent discontinuation of study drug or reference drug	X3 ^{#2}	X1 ^{#2}	X2 ^{#2}
Drug related TEAEs leading to permanent discontinuation of study drug or reference drug		X1	
Serious TEAEs leading to permanent discontinuation of study drug or reference drug		X1	

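### As written, the Week 12–52 adverse-event percentages keep pre-Week 12 leavers in the 100 mg, 150 mg and etanercept denominators but not in the placebo-switch denominators

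*SAP*

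**What the plan says.** SAP 7.1 (Table 4 and the definitions below it) sets up five Treatment Sequence groups with two different entry rules.

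- **Continuous groups.** Entry depends on initial treatment only: "100 mg: subjects who initially treated as ASP015K 100 mg Group". The 150 mg group has the same wording, and so does the reference group: "Etanercept: subjects who initially treated as Etanercept Group".
- **Switch groups.** Entry needs exposure after the switch: "switched ASP015K 100 mg at Week 12 and at least one dose of ASP015K 100 mg drug after switched". The 150 mg switch group is worded the same way.

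SAP 7.5 states that the adverse-event analysis from Week 12 onward "will be performed by Treatment Sequence Set in SAF". Membership of SAF is wide (SAP 5.3): "SAF is defined as all subjects who received at least 1 dose of the study drug or reference drug".

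Tables 20 and 21 in SAP Appendix 3 mark their Week 12–52 column for the five groups together: "X2: 100mg, 150mg, Placebo to 100 mg at Week 12, Placebo to 150 mg at Week12, Reference". Table 20 gives the number and percentage of subjects with TEAEs, deaths, serious TEAEs, Grade 3 or higher TEAEs and TEAEs leading to discontinuation. Table 21 gives the main SOC/PT tables, including the list of TEAEs above 5% in any group.

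No SAP text limits the denominator of that column to subjects still on treatment at Week 12.

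**The concern.** A post-Week 12 exposure condition applies to two of five columns printed side by side. A subject on 100 mg who stopped at Week 6 counts in the Week 12–52 denominator, with little or no chance of an event in that period. A placebo subject who stopped at Week 6 counts in no sequence group. With equal risk per treated subject, continuous ASP015K and etanercept would appear to have fewer events than newly switched ASP015K.

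The later-period percentage also matters within an arm. The sample-size rationale (SAP 4) cites seeing whether common events become more frequent late in treatment. A denominator that includes subjects no longer treated works against that.

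The patient-year analysis does not repair the column. SAP 7.5.1 says these rates will be shown for the same periods and overall, but Table 22 lists only Week 0–12 and Overall. SAP 7.5.1.2 counts duration from the initial dose, not from Week 12.

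**Working it through.** **Plan's own figure.** The documents give no number for the Week 12–52 denominators. The nearest safety figure is the 95% chance of seeing at least one subject with an event of 1.5% incidence among 200 reference subjects (SAP 4). It reproduces: 1 − 0.985^200 = 0.951. It refers to the full reference group, not to those treated after Week 12.

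**Inputs**
- Planned group sizes: 100 per study-drug group, 200 etanercept (SAP 4).
- Share leaving before Week 12, d: not stated for RAJ3. As a proxy, adverse-event discontinuations in RAJ1 were 10.9% at 100 mg, 6.9% at 150 mg and 17.9% on placebo (Protocol 1.3). There is no such figure for etanercept. Assumed range for all three continuous groups: 5% to 20%.
- True Week 12–52 incidence per treated subject, p: not stated. 20% and 50% are used for illustration.

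**Formula.** If leavers have no event in the period, reported percentage = p × (1 − d). In the switch groups, reported percentage = p.

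| d | (1 − d) | p = 50% reads | p = 20% reads |
|---|---|---|---|
| 5% (assumed) | 0.950 | 47.5% | 19.0% |
| 6.9% (RAJ1, 150 mg) | 0.931 | 46.6% | 18.6% |
| 10.9% (RAJ1, 100 mg) | 0.891 | 44.6% | 17.8% |
| 20% (assumed) | 0.800 | 40.0% | 16.0% |

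At equal true risk, the continuous-to-switch ratio reads 0.95 to 0.80 instead of 1.00. Subjects treated after Week 12 would number 95 to 80 of 100 per ASP015K group and 190 to 160 of 200 on etanercept.

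**Effect on the 5% listing.** With 11 early leavers of 100, 5 subjects with an event are 5/89 = 5.6% of those treated (listed) but 5/100 = 5.0% as planned (not above 5%, so not listed unless another group qualifies).

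**Follow-up.** SAP 6.2 ends the TEAE window at Week 52 or withdrawal, but SAP 7.5.1 extends it through follow-up. Under the second rule, a subject who left shortly before Week 12 could still add an event after Week 12, so the dilution is slightly smaller than the full (1 − d).

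**Efficacy at end of treatment.** Table 19 rows 1.1.2, 3.2 and 11.1.2 show all five groups at EOT, and the EOT window opens on Day 2 (SAP 7.11.5). Early leavers therefore count in the continuous groups, while placebo leavers are in no group. For a response rate, the shift is d × (stayers' rate − leavers' rate). With an assumed gap of 50 points, that is 0.109 × 50 = 5.5 points at the RAJ1 100 mg rate, and 2.5 to 10 points for d of 5% to 20%.

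**The case against.** Several objections have force.

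- **The denominator is inferred.** The SAP does not write it out. SAP 7.1 refers table formats to separate TLF specifications, which are not among the documents and could set an at-risk count. A reader might infer that the percentages will certainly be diluted. The documents support only that the rule, followed as written, produces this.
- **The tables are descriptive.** SAP 7.1 calls the switch groups optional and outside the primary objective, and all planned tests are against placebo. This stands, although Tables 20 and 21 do schedule the five-group columns.
- **Long-term safety is mainly shown elsewhere.** A reader might infer that the 52-week safety assessment as a whole is biased. The documents do not support that. The Overall column in Table 20 uses the X3 groups (100 mg, 150 mg, reference), which share one entry rule. Overall patient-year rates are planned expressly to allow for differing duration and dropout. The special-interest events in Table 21 have no Week 12–52 entry.
- **The efficacy effect is narrow.** A reader might extend the problem to all Week 52 efficacy. Most Week 52 rows of Table 19 omit the switch groups, and from Week 16 early leavers have no data of their own in the visit windows. The point concerns the EOT cell of three untested rows.
- **The size is borrowed.** RAJ1 tested a single agent, and worsening RA was the main reason for discontinuation (21 of 32). RAJ3 allows concomitant DMARDs, so the RAJ1 rates are not a proven lower bound for RAJ3. For rarer events the absolute change is small: 5.5% × 0.891 = 4.9%.
- **Attrition is visible.** Disposition (SAP 7.2.1) and exposure categories (SAP 7.3.1) would let a careful reader see early losses.

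These points limit the reach and size. They do not remove the unequal entry rule or supply a Week 12–52 rate with a consistent denominator.

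**Conclusion.** The point holds for the Week 12–52 columns of Tables 20 and 21. Following SAP 7.1, 7.5 and 5.3 as written, the percentages in the 100 mg, 150 mg and etanercept groups understate incidence per treated subject by about (1 − d), while the two switch groups carry no such reduction. The relative understatement is about 7% (150 mg) to 11% (100 mg) if RAJ3 attrition matches the RAJ1 adverse-event discontinuation rates, and 5–20% over the assumed range. Etanercept has only the assumed range.

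This rests on two assumptions: the percentage denominator is the group count within SAF, and leavers contribute few or no events after Week 12. The primary ACR20 analysis, the Week 0–12 tables, the Overall tables on the X3 groups and the overall patient-year rates are unaffected. It should be corrected before the tables are produced, but it does not threaten the trial's main conclusions.

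**What to change.** In SAP 7.1 and Tables 20–21, define the denominator of every Week 12–52 column, in all five groups, as subjects with at least one dose at or after the Week 12 visit. Add a footnote that it differs from the Week 0–12 denominator. For the EOT cell of Table 19 rows 1.1.2, 3.2 and 11.1.2, use the same set in every group shown side by side.

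Do not equalise the safety tables by assigning every placebo subject to a switch group according to the dose randomised at baseline. That adds subjects never exposed to ASP015K: at the RAJ1 placebo discontinuation rate, a true 80% would read 0.80 × (1 − 0.179) = 65.7%, so the dilution would spread to all five groups.

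The cost is one sentence, one programming flag and a footnote. Equal denominators still leave subjects who have tolerated 12 weeks of drug beside newly exposed ones, so the columns remain descriptive.

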7.2 Study Population

7.2.1 Disposition of Subjects

The following subject data will be summarized and presented with regard to All Subjects with Screening Failure Log and Case Report Form.

- Screened
- Screen failed
- Randomized

The following subject data will be summarized and presented by Initial Randomization Set and Treatment Sequence Set:

- Subjects randomized and dosed (same as the FAS)
- Subjects who prematurely discontinued from the study period during overall period
- Subjects who prematurely discontinued from the study period by 4 weeks
- Subjects who included/excluded of FAS, PPS, SAF, PKAS, and PDAS

These analyses are also conducted by Study Region and Protocol Version Number (used for confirmation of the Inclusion criteria and the Exclusion criteria).

The following analysis will be conducted for Initial Randomization Set.

- For time-to-withdrawal from initial dose up to Day 92: Kaplan-Meier plot will be constructed.

Withdrawal Due to Lack of Efficacy:

In addition to the disposition summaries, the percentage of subject withdrawal due to lack of efficacy as the primary reason for withdrawal will be presented for all groups and compared (each ASP015K dose group versus placebo) using Fisher's exact test, and the analysis will be based on SAF by Initial Randomization Set. Fisher's exact p-values (No multiplicity adjustment) will be provided.

The following subject data will be summarized and presented by Initial Randomization Set and Treatment Sequence Set

- Subjects who discontinued after starting the study period will be summarized for primary reason for withdrawal during overall period. This analysis is also conducted by Study Region.
- Subjects who discontinued after starting the study period will be summarized for primary reason for withdrawal by 4 weeks.
- Subjects who were excluded from FAS, PPS, SAF, PKAS, and PDAS will be summarized by reason for exclusion.

7.2.2 Demographic and Other Baseline Characteristics

All demographic and other baseline characteristics (defined below) will be summarized by treatment group. To explore the imbalance among treatment groups (except for reference group), comparisons with respect to categorical variables (e.g., sex) will be based on chi-squared test (continuity corrected), and comparisons with respect to continuous variables (e.g., BMI) will be based on a one-way ANOVA model with fixed effect for treatment group. All analyses/summaries except for (7.2.2.4) will be based on the SAF and PPS.

If the imbalance of the factors between treatment groups is found (at a two-sided 0.05 significance level) and considered to clinically affect the primary variable, an analysis adjusted for the factor will be performed to assess the effect of the primary variable on the primary analysis.

